4 TRIAL STRATEGIES

4.1 Intervention

Participants randomised to the intervention group will attend a 6-week GL course in their local area co-delivered by professional facilitators and peer-tutors living with dementia. Professional facilitators will be staff working for one of the delivery partners listed under Phase 2, following the manual and facilitator training developed in Phase 1.

Two professional facilitators for each site will attend a 2-day training workshop run by LiD. They will receive the Good Life manual and be supported throughout the set up and delivery of the course in their local area by LiD through online supervision meetings. Peer-tutors (2 per site) will be people living with dementia already known to services who will be supported to tailor the course to local needs and co-deliver sessions alongside professional facilitators. Peer-tutors will be invited to participate in the embedded qualitative study looking at the feasibility of intervention delivery but will not be participants in the trial and thus do not need to meet the inclusion criterion of having been diagnosed in the previous 12 months. It will be

the responsibility of delivery sites to recruit and support peer-tutors, not recruitment sites or the research team.

Tailoring of the course will be done through 3 in person co-production sessions between the facilitators and peer-tutors. Across these meetings, priorities are agreed and a plan for content over the six sessions of the course is devised. Throughout this time, the tutors have the opportunity to ask questions and discuss concerns with the facilitators, either in the group meetings or individually after. They also plan how they would like to be involved in delivery of the course. This could involve introducing speakers, sharing their own experiences and/or fielding participants' questions. In all these activities they will be supported by the professional facilitators. A member of the research team may attend one or more of these co-production meetings to assess fidelity. After each co-production meeting a summary of what was discussed is mailed out to peer-tutors for reference/to support recall. Between and after co-production sessions, facilitators invite experts and local services to speak on the course and answer participants' questions.

Prior to the course starting each participant randomised to the intervention arm will be contacted by the professional facilitators and a pre-course visit (or equivalent contact) arranged. This allows facilitators to introduce themselves and the course and to answer participants' queries about how the course works and check on travel needs and any accessibility requirements. This is an essential part of the model, supporting building of rapport, alleviating anxiety thereby promoting course attendance.

Each session will involve a pre-planning element with peer-tutors to write scripts and support peer-tutors in preparation for the session. During the course sessions the non-judgemental ethos of the course and equal value of everyone's knowledge and experience is emphasised. Peer-tutors are not expected to have all the answers, rather the course is an opportunity to learn and share together. A key part of the preparatory sessions is discussing how the tutors might feel if a participant on the course becomes upset or raises a sensitive issue. Whilst lived experience positions peer-tutors well to respond with empathy to the challenges faced by peers, it is not peer-tutors' responsibility to manage safeguarding or the emotional wellbeing of participants, this is the role of the professional facilitators and the wider service they work for, and established safeguarding procedures of individual organisation will be followed.

After each of the six sessions there will be an opportunity for peer-tutors to debrief with the professional facilitator and input into the session summary letter which will be sent out to all participants (including peer-tutors). This provides ongoing support for peer tutors and a

record of what was discussed for the participants. An end of course resource pack is produced for all attendees.

After the course, facilitators will work with learners and tutors to plan 'next steps'. Options will be different in different areas, but one possibility is that learners from the initial course become tutors on a future course. We will capture 'next steps' qualitatively, measuring outcomes of these additional opportunities for study participants will be tested for feasibility at 6-months.

Delivery in the South Asian site will be undertaken by LMCP with translated materials and tailored language support.

The GL model advocates reimbursing peer-tutors for their time attending co-production sessions and co-facilitating the course sessions. We will be adopting this policy for the trial, using INVOLVE rated (£25 per hour).

Fidelity of the intervention is an important consideration when planning for a larger trial. iID will assess fidelity against the manual checklist and researchers will observe at least one co-production meeting and one course session in each locality, recording details of delivery and tailoring to produce the TIDieR checklist. The course will run weekly for 2 hours (with a break) at an accessible venue. Carers will not be invited to take part in the training, but a buddy or personal assistant can accompany the person if required, and there will be a separate space for carers to congregate and socialise during each session

4.2 Control

Individuals randomised to usual care will not receive any additional services and will be asked not to attend an official GL course until 6-month data collection is complete. We will ask both groups to report on all services and groups attended over the 6-month period to improve our understanding of usual care, using a bespoke tool informed by the CSRI. Learning about usual care will be interpreted in light of learning from the wider DeNPRU-QM study to reduce duplication of effort.

5 DATA COLLECTION

5.1 Schedule of data collection

Data collection will focus on feasibility of administration of the outcome measures detailed in section 2.3, together with demographics and service use data collection. Members of the research team will collect demographic and baseline outcomes data prior to randomisation. The data will be collected with a flexible approach dependent upon the request of the

participant. This could be face to face or remote via an online platform or telephone. The first session is likely to be face-to-face (to build trust and enable communication), but if a person has a clear preference for remote communication from the outset this will be possible. All questionnaires will be administered by a member of the research team. The questions will be asked by the researcher (with visual aids showing scales where appropriate) and the participant's answer inputted into online questionnaires on a tablet.

Adaptations for reduced capacity: If a participant loses the capacity to give informed consent but still assents to attempting the measures (and a consultee advises that they would wish to remain in the study) the researcher will proceed but be particularly alert to signs of fatigue, distress or confusion. Whilst in general we will approach data collection in a standardised way (administering the same measures in the same way) for people with reduced capacity there will be the flexibility to amend the questionnaire order and use short versions. For example, we would start with the most dementia friendly measure (My Life Questionnaire) and we could replace the full Geriatric Depression Scale (GDS) with the 4 item GDS screening tool. Finding ways to make participation possible for as a broad a group as possible is a key aim of this inclusive feasibility study and so rather than rule out flexibility we will allow this where warranted and note the consequences (for feasibility, data quality and participant experience).

Adaptation for SA participants: If required for interpretation, LMCP will support at the consent and baseline data collection point. If further support is required for the subsequent data collection, then a professional interpreter will be employed. Baseline data collection happens pre randomisation and therefore LMCP can support with this and support building of relationships between participants and researcher. Once allocation takes place LMCP's role is intervention delivery only.

Two subsequent data collection points will be on completion of the GL course and 6 months post baseline.

Participants randomised to the intervention arm will complete an 'in the moment' short wellbeing questionnaire (the Canterbury Wellbeing Scale) before and after each course session, facilitated by the professional facilitators.

5.1.1 Baseline data

Prior to randomisation baseline data will be collected by a member of the research team. Demographic information collected will include:

- Contact details of emergency contact who could act as consultee (if consented to)
- GP details (if consented to)
- Date of birth
- Gender
- Living situation (with others, living on own)
- Type of dementia
- Co-morbidities
- Ethnicity
- Details of usual residence (own home, supported living)
- Time since diagnosis (if known)
- Time since first noticed difficulties
- Time since initial help seeking (e.g. contacted GP about potential dementia symptoms)

The baseline questionnaires will contain the following:

- Demographics
- Usual care
- ICECAP-O
- My Life Questionnaire (MLQ)
- EQ-5D-5L
- Geriatric Depression Scale
- De Jong Gierveld Loneliness Scale

The questionnaires will be administered in the order above (to assess acceptability with the primary outcome measure ICECAP-O being asked first) unless there is justification for adaptation (for example because of fatigue or reduced capacity – see above) in which case these reasons and any action taken will be noted. .

5.1.2 Intervention period

Participants randomised to the intervention arm will be contacted by the course facilitators in their locality and then supported to attend a 6-week course, for 2 hours with a break each week. Each week the Canterbury wellbeing scale will be administered at the start and end of each session by the course facilitators. Training in how to administer this scale will form part of the 2-day facilitator training package. The facilitators will support the participants to complete the scale, reading out the questions to the group and the participants individually

completing a paper version of the scale. The group facilitators will collect these at the end of the sessions and store them securely until a member of the research team collects them at a site visit.

Attendance figures will also be collected during the course, along with any reasons given for non-attendance.

5.1.3 Course completion data collection

At course completion a researcher will visit each participant (both arms of trial) or make other arrangements to collect follow up data. The questionnaires used at baseline (except demographic information) will be repeated in the same order. A sub-set of participants will be purposively sampled and invited to take part in qualitative interviews, see 5.5 for further details.

5.1.4 Six month follow up

The 6 month follow up will be 6 months from baseline data collection and will include the same questionnaires as at course completion for both arms of the trial.

5.2 Feasibility of implementation

As part of assessing the feasibility of implementation we will invite professional facilitators and peer-tutors to take part in qualitative interviews on completion of the intervention delivery. At this point we will also collect some demographic and context information from the professional facilitators and peer tutors (with their consent). During the two-day training the professional facilitators will be made aware that some of the sessions will be observed to assess fidelity of the intervention. When recruiting peer tutors the professional facilitators will clearly explain that this iteration of the Good Life course is part of a research project and a researcher may be present at some course sessions to see how it is being delivered, but they will not be collecting any data from peer-tutors (unless they consent to take part in a qualitative interview after the course).

5.3 Embedded qualitative study

The qualitative part of the study will include in-depth interviews with people with dementia and carers. For participants with dementia who consented to a family member or friend who

supports them being informed of the study and interviews we will send out a summary of the interview, what is involved and a consent to contact form for them to return if they are interested in finding out more. We will purposively sample both groups to ensure a range of diverse participant experience is included such as ethnicity, and living situation (living alone or with carer, for instance). Interpreters will support qualitative interviews where needed.

The interviews will be flexible in approach. Those with people with dementia will most likely will be face to face, unless telephone or online is requested.

We will invite all delivery partners (professional facilitators and any other staff involved in delivery) to take part in an online focus group. Peer tutors will be invited to take part in individual interviews most likely face to face.

A sub-set of recruitment staff will be invited to take part in an online interview.

All interviews will last 30-45 mins and the focus group 60-90 minutes. They will be audio recorded using an encrypted voice recorder. Audio recordings will be transcribed by a University of York approved transcription service. Topic guides will be used for the differing groups of participants and informed by the study aims developed with input from the project management group and advisors with lived experience.

5.3.1 Qualitative focus group with delivery partners

Professional facilitators (n=6) from the 3 sites will take part in an online focus group. Topics for delivery partners will include barriers and facilitators to GL implementation, study processes and inclusiveness. The delivery partner focus group will take place after course completion.

5.3.2 Qualitative interviews with peer tutors

Peer tutors (n=6) will be invited to take part in a one-off individual interview. Topics covered in the interviews will include becoming a peer tutor, co-producing their local course and jointly delivering the course sessions with professional facilitators. The peer tutors will be invited for interview at the end of the Good Life course.

5.3.3 Qualitative interviews with carers

Family members or others identified as 'carers' will be invited to be interviewed about their role in supporting recruitment, retention, adherence to GL and any knock-on benefits or

harms, recognizing that people with dementia live interdependent lives [23]. Carers can be interviewed in a dyad with the person with dementia that they support if this is requested.

Carers will be sent a summary of the interviews and can express interest by returning a consent to contact form when they are informed of the person, they support participation in the research.

We will interview n=15 carers across both arms of the trial, the intervention arm and UC arm.

It is important to interview carers from both arms of the trial to gain a picture of how supporting recruitment and study retention is affected by the randomisation process. Carers will be invited for interview after course completion data collection.

5.3.4 Qualitative interviews with participants with dementia

Participants with dementia will be interviewed about their views and experiences of the study including initial contact, processes of recruitment, randomisation, experiences of providing data (including measure acceptability and applicability), attending the intervention (where applicable) and the inclusiveness of all study processes.

Participants will be interviewed from both trial arms n=15 and can be interviewed in a dyad with their carer if requested. Participants with dementia who do not have a named carer will be purposively selected to understand any implications of not having this support.

For the embedded qualitative element separate participant information sheets detailing what is involved in this part of the study will be provided to potential participants and separate informed consent will be obtained for this part of the study. We will only invite people for interview who agreed on their trial consent form that they were happy to be contacted about this part of the study.

5.3.5 Qualitative interviews with recruitment staff

The recruitment staff will provide ongoing information about the success or otherwise of recruitment strategies through the site-specific screening log. Data will also be gathered through ongoing check in conversations, email conversations, any site visits or attending team meetings to discuss trial processes. Information on recruitment will be collated onto a simple framework on excel. We will also invite a subset of staff to take part in a qualitative interview or focus group. Topics covered in the interviews/focus group will include reasons for success or otherwise of recruitment strategies, inclusiveness and suggestions for improvements required for a full trial.

5.3.6 Informed consent for the qualitative study

The people with dementia will be informed about the interviews in the feasibility study PIS and if they are happy to be contacted about the interviews, they can indicate this on the feasibility study consent form. Carers will be informed of the opportunity to take part in an interview via letter or email. If they have consented to be contacted with further information about taking part in an interview, we will send them the information sheet. The delivery partners and peer-tutors will be approached by the research team towards the end of intervention delivery with information about the qualitative study and asked if they would be willing to take part.

The peer tutors will be provided with a separate participant information sheet to the professional facilitators for the interviews. This will provide information about what is involved in taking part in a qualitative interview, including audio recording and transcription of the interviews. Agreeing to be a peer-tutor does not imply they will take part in a qualitative interview, we will make clear throughout that this would be voluntary. Full information will be given at least a week before the interview to give time to make a decision, and informed consent will be sought immediately before the qualitative interview.

Potential participants across all groups who are selected to be invited for an interview will be contacted by a researcher and details about what is involved explained along with receiving the PIS. Informed consent will be flexible as per the processes used for the feasibility study (section 3.5) dependent upon the request of the participant. For members of the SA community (people with dementia and carers) we are developing inclusive research materials as part of phase 2 of the research, this is an ongoing piece of work.

There is more likelihood to have remote data collection in this qualitative part of the study. Both carers and recruitment staff may prefer to have either a telephone or online interview due to other commitments. The focus groups with staff will be online due to the dispersed geography of staff. The consent processes for remote interviews/focus groups will vary based on preference and digital skills. If the potential participant has an email address and is confident to complete a consent form electronically returning it to the researcher, then informed consent can be completed electronically. In this instance both the returned completed consent form and a copy of the accompanying email will be stored securely to produce an audit trail. If the potential participant is not confident in using email, then informed consent can be obtained verbally and audio recorded. The consent form would be read out by the researcher and the participant would verbally agree or disagree with each statement, completing the consent process by stating verbally their full name and whether

they consent to take part in the research or not. This would then be stored securely on the University of York server separate to any data.

5.4 Assessing the fidelity of the intervention

One of the research questions for this trial is whether the Good Life course can be manualised and delivered consistently across differing community settings. The fidelity of the courses will be assessed in the following ways.

Throughout the set up and delivery of the course the professional facilitators will have monthly online supervision sessions with IiD, these will give the opportunity for any difficulties arising from adhering to the core constructs or deviations from the manual to be documented and addressed. A fidelity self-report checklist will be used to check adherence to the core constructs and manual for the course, this will be devised after Phase 1 (manualisation and training development) with input from the PMG. This checklist will be completed after each course session by the professional facilitators and will be written into the sub-contracts for each site.

At least one pre-course coproduction meeting and one course session per site will be observed by a member of the research team and the same checklist completed by the researcher for that session for comparison. The observation of the session will be to assess fidelity of the intervention to the manual and core constructs only. Information that some sessions may be observed for fidelity will be included in the participant information sheet for the trial. The observations will not be audio or video recorded; the researcher will be assessing fidelity only, not collecting data.

The researcher will provide a reminder on the day of the observation explaining what it is for. For clarity it is the facilitators who are being observed to see how they deliver the course and whether it is consistent across all settings and with the manual.

The qualitative interviews with delivery partners and peer tutors will provide further insight into the fidelity of the intervention.

6 DATA ANALYSIS

6.1 Quantitative data

The quantitative data will be analysed using descriptive statistics. Mean and standard deviations for key outcomes will be calculated to support subsequent power calculations for

the full trial. Whilst any difference between intervention and control groups might support our case for the ‘promise’ of the intervention, it will not be used as a basis for estimating required sample sizes.

Data will be reported in line with CONSORT guidance extension to feasibility studies. We will assess the feasibility and acceptability of the trial design by calculating proportion of participants:

- Consenting from those eligible/approached
- completing baseline and follow up measures
- completing the intervention - i.e. attending at least 4 out of the 6 sessions.
- completing in the moment wellbeing questionnaires

In line with CONSORT guidance, we will additionally report the proportion of complete data at each timepoint for each measure.

6.1.1 Criteria for progression to full RCT

Descriptive data on recruitment, retention, response rates and adherence to the course will be framed against the below, traffic-lit progression criteria:

	Participants	Action
Go (Green)	
a) Recruitment: ≥ 45 participants with dementia recruited in 7-month period (equates to $>83\%$ of desired sample of 54)
 
b) Retention: $\geq 75\%$ of recruited participants remain in the study (excluding deaths)
 
c) Data collection: $\geq 75\%$ provide data at each time point
 
d) Adherence: $\geq 75\%$ of intervention group adhere to the intervention
	Continue to full trial
Amend (Amber)	
a) Recruitment: 30 to 44 participants recruited
 
b) Retention: 50-74% remain in the study (excluding deaths)
 
c) Data collection: 50-74% provide data at each time point
 
d) Adherence: 50-74% adhere to the intervention
	Proceed with adaptations
Stop (Red)	
a) Recruitment: < 27 participants ($< 50\%$ of expected sample)
 
b) Retention: $< 50\%$ remain in the study (excluding deaths)
 
c) Data collection: $< 50\%$ provide data at each time point
 
d) Adherence: $< 50\%$ adhere to the intervention
	Consider not proceeding

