3.3.3 Phase 3: Feasibility trial (month 8-27)

Phase 3 will include the training of professional facilitators working for delivery partners in each of the three localities, support of local people living with dementia to become peer-tutors, recruitment of eligible participants to the trial through sites and participant identification centres (PICs), and delivery of the Good Life course to participants randomised to the intervention group.

54 participants will be recruited across 3 sites (18 per site) and informed consent collected. Baseline data collection will take place prior to randomisation on a 2:1 ratio (intervention or usual care). For those randomised into the intervention group they will attend a 6-week Good Life course in their local area. Upon course completion both arms of the trial (intervention or usual care) will have a researcher visit them to collect follow up data. The final data collection point will be at 6-months post baseline apart from a sub-set of participants with dementia who will be invited to a qualitative interview about their experiences of taking part in the research.

Facilitator training will be delivered by Innovations in Dementia (IiD) alongside people with lived experience of dementia. The trainee facilitators will receive a copy of the manual and be supported throughout the set up and running of the course via online monthly supervisions by IiD. Course set up includes the identification and support of peer tutors (people with dementia who are *not* trial participants) and co-production sessions to tailor the course to the local context. It also includes a home visit or equivalent contact with each participant in the intervention group in advance of the course to answer questions and build trust. The course runs for six sessions, meeting as a group in-person, co-facilitated by trained facilitators and peer-tutors living with dementia. Fidelity of the course will be assessed by IiD against agreed criteria aligned with the core constructs in the manual, and by course observation by the research team (at least one session to be observed in each location). For detailed information on the intervention see 4.1

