3.6 Randomisation

Once enough participants have been recruited in an area (18 per locality) and informed consent has confirmed, the baseline data will be collected. Upon completion of all the baseline data for that site randomisation will take place. Only participants who have given informed consent and completed the baseline data collection will be randomised.

Participants for each site will be randomised individually once the recruitment target (18) has been reached. This will allow for staggered starts of the intervention.

Randomisation will be undertaken to a ratio of 2:1, with 12 people randomised to the intervention and 6 to usual care in each study site. An unequal ratio is being used to allow greater numbers to the intervention arm to help incentivise recruitment. Sealed Envelope software [21] will be used to carry out the randomisation.

The researcher will enter brief participant details (study ID, study site, and date of informed consent) into the online randomisation site. The online tool will indicate which participants have been allocated to which group (intervention or usual care). The researcher will then inform the participants personally rather than an automated email being sent.

Upon completion of the randomisation process the researcher will inform the participants of the outcome via telephone or the participant's preferred method of communication. This will be confirmed in a letter or email to the participants. Delivery partners will be given the names and contact details of the participants in the intervention group via a secure means. They will then contact the participants allocated to the group following guidance from the course manual.

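### The retention criterion, and by inference the data-collection criterion, is pooled over a 2:1 allocation, so the traffic light can read Green with usual-care follow-up below 50%

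*Protocol*

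**What the plan says.** Protocol 6.1.1 sets four traffic-light criteria. Retention (b) is Green at 75% or more "of recruited participants remain in the study (excluding deaths"), Amber at 50-74% and Red below 50%. Data collection (c) uses the same cut-offs for the share who "provide data at each time point" and gives no denominator. Adherence (d) is the only criterion tied to one arm, the intervention group.

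The outcome table in 2.3 defines completion of measures over all recruited people with dementia, and 6.1 speaks of the proportion of participants. Nowhere is there a usual-care threshold or a limit on the difference between arms.

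Section 3.3.3 plans that "54 participants will be recruited across 3 sites (18 per site) and informed consent collected". Section 3.6 allocates 2:1, "with 12 people randomised to the intervention and 6 to usual care in each study site", and gives the reason: "An unequal ratio is being used to allow greater numbers to the intervention arm to help incentivise recruitment". Section 4.2 states: "Individuals randomised to usual care will not receive any additional services".

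**The concern.** A pooled percentage weights each arm by its size, so the intervention arm supplies two thirds of the retention figure and usual care one third. Good retention in the larger arm can offset poor retention in the smaller one.

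There is some reason to think losses could fall on usual care. Section 4.1 gives the intervention arm a pre-course contact, six weekly sessions and summary letters. Section 4.2 gives usual care nothing extra and asks those participants to stay off an official course until the 6-month data are in.

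The study exists to judge whether a randomised comparison is feasible (2.2), and estimating retention is a primary objective. A comparison needs follow-up in both arms, and unequal loss could bias it, depending on why people leave. A rule that can recommend going ahead when under half of the controls were followed up does not test this.

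**Working it through.** **Inputs.** 54 recruited, 18 at each of 3 sites (3.3.3). Arms of 12 and 6 per site (3.6), so 3 × 12 = 36 and 3 × 6 = 18. Green at 75% or more, Red below 50% (6.1.1). For the enumeration I assume that all 54 are randomised and nobody dies.

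**The plan's own figures.** 45/54 = 83.3%, which matches the stated Green recruitment share, and 27/54 = 50% matches the Red one. There is no power-based sample size to reproduce.

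**Pooled Green.** 0.75 × 54 = 40.5, so 41 are needed (41/54 = 75.9%; 40/54 = 74.1%).

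**Usual care in Red.** Below 50% of 18 means 8 or fewer (8/18 = 44.4%).

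**Both together.** The intervention arm must retain at least 41 − 8 = 33 of 36 (91.7%). The possible splits are:

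| Intervention retained | Usual care retained, pooled Green and usual care Red |
|---|---|
| 33/36 (91.7%) | 8/18 |
| 34/36 (94.4%) | 7 or 8/18 |
| 35/36 (97.2%) | 6 to 8/18 |
| 36/36 (100%) | 5 to 8/18 (5/18 = 27.8%) |

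**At the Green recruitment minimum of 45 (30:15 if 2:1 is kept).** Green needs 34. 27/30 + 7/15 = 34/45 = 75.6% is Green with usual care at 46.7%. The lowest case is 30/30 + 4/15 (26.7%).

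**The reverse.** 17/36 + 18/18 = 35/54 = 64.8%, which is Amber. An intervention arm in Red cannot reach pooled Green.

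**Probabilities.** Let I be Binomial(36, p1) and C be Binomial(18, p2), independent. The quantities are P(I + C ≥ 41), P(I + C ≥ 41 and C ≤ 8), and P(I + C ≥ 41 and C ≤ 13); 13/18 = 72.2% is the largest count below 75%. The true rates are assumptions, since the protocol gives none.

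| p1 v p2 | Pooled Green | Green, usual care <50% | Green, usual care <75% |
|---|---|---|---|
| 95% v 45% | 0.77 | 0.35 | 0.76 |
| 95% v 50% | 0.86 | 0.28 | 0.85 |
| 90% v 50% | 0.63 | 0.13 | 0.62 |
| 90% v 60% | 0.84 | 0.05 | 0.74 |
| 90% v 70% | 0.95 | 0.01 | 0.62 |
| 80% v 80% | 0.82 | <0.001 | 0.17 |

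**Two possible remedies compared when the arms do not differ.**
- Requiring 75% in each arm means at least 27/36 and 14/18. P(Green) falls from 0.82 to 0.60 at a true 80%, from 0.51 to 0.31 at 75%, and from 0.97 to 0.85 at 85%.
- Capping at Amber when an arm is below 50% is triggered by usual care with probability P(C ≤ 8) = 0.0009 at 80%, 0.005 at 75% and 0.02 at 70%.

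**The case against.** A reader might infer that the plan hides differential drop-out. The documents do not support that. Attrition and loss to follow-up are feasibility outcomes (2.3), participant flow follows CONSORT (3.7), and reporting follows its feasibility extension (6.1). Carers from both arms are interviewed on how randomisation affects retention (5.3.3), and qualitative findings are weighed alongside the numbers (6.2). Red only advises considering not to proceed, so the rule is not mechanical. All of this stands. What remains is that none of it changes the traffic-light rating.

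A reader might also infer that the protocol expects usual care to drop out more. It does not say so. The 2:1 ratio is justified by recruitment, not retention, and researchers follow up both arms. A large gap is an assumption, and Green with usual care below 50% needs at least 33/36 retained in the intervention arm. That limits the likelihood but not the logical gap.

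The denominator objection also stands. Criterion (b) counts recruited people, some of whom may leave before randomisation (3.4.1) and so have no arm. Baseline data are required for randomisation (3.6), so arm differences in (c) can arise only at course completion and 6 months. A by-arm figure must be defined on randomised participants.

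By-arm tables could be left to an analysis plan. The progression rule is different: its thresholds and actions are fixed in the protocol.

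**Conclusion.** The point holds as a limited defect in the decision rule. With 36 and 18 per arm, criterion (b) can be Green with usual care anywhere from 5/18 to 8/18. The same arithmetic applies to (c) at each follow-up if, as appears, it is pooled too. The gap is one-sided: only usual care can be below 50% while the pooled figure is Green.

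The enumeration is certain given those arm sizes. The likelihood is not: from about 0.35 down to 0.01 across the unequal scenarios shown, under independent binomial retention at assumed rates. Masking of a milder shortfall is more likely, with usual care below 75% in 0.74 of trials at 90% v 60%. With only 18 controls, however, that also happens in 0.17 of trials when both arms truly retain 80%.

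It would go too far to conclude that each arm must reach 75%, or that an arm below 50% should be an automatic Red. An observed 8/18 has an exact 95% CI of 22% to 69%, too wide to carry a stop rule.

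**What to change.** In 6.1.1, keep the pooled thresholds and add three things:

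1. Calculate (b) and (c) by arm as well, among randomised participants, at course completion and at 6 months.
2. Report the between-arm difference with its 95% CI.
3. State that a criterion cannot be rated Green, and is at most Amber, if either arm is below 50%.

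Do not require 75% in each arm, and do not add an automatic per-arm Red.

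This takes a few lines of text and no new data. It should be settled before outcome data are seen, because a by-arm condition added later would be post hoc. The cost is reliance on a small arm: one person in 18 moves the usual-care figure by 1/18 = 5.6 points. False triggering is rare, about 0.1% at a true 80%. The cap does not catch usual care at 50-74%; the reported difference and its interval have to show that.
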